**Immune-Related Response Criteria Definitions**

Target Lesion Definition	Non-Target Lesion Definition	New Measurable Lesions	New Unmeasurable Lesions	Percent change in tumor burden (including measurable new lesions when present)	Overall irRC Response
Complete Response	Complete Response	No	No	-100%	irCR
Partial Response	Any	Any	Any	≥ -50%	irPR
				<-50% to <+25%	irSD
				>+25%	irPD
Stable Disease	Any	Any	Any	<-50% to <+25%	irSD
				>+25%	irPD
Progressive Disease	Any	Any	Any	≥+25%	irPD

11.4.1.5 Immune-Related Best Overall Response Using irRC (irBOR)

irBOR is the best confirmed overall response over the study as a whole, recorded between the date of first dose until the last tumor assessment before subsequent therapy (except for local palliative radiotherapy for painful bone lesions) for the individual subject in the study. For the assessment of irBOR, all available assessments per subject are considered.

irCR or irPR determinations included in the irBOR assessment must be confirmed by a second (confirmatory) evaluation meeting the criteria for response and performed no less than 4 weeks after the criteria for response are first met.

[figure not shown]
11.4.2 Definition of immunotherapy Response Assessment in Neuro-Oncology (iRANO)

Standard RANO criteria differ according to whether the target population is high-grade

glioma, low-grade brain tumors, or solid tumor brain metastases [Lin *et al.*, 2015] [Wen *et al.*, 2010, Van Den Bent *et al.*, 2011] Given the clinical success of modern immunotherapy trials, iRANO was designed to integrate seamlessly into these different “backbone” RANO criteria (Okada *et al.*, 2015). iRANO takes an algorithmic approach as to whether a patient may remain on protocol therapy following the first “disease progression” event after beginning protocol therapy, and provides the ability for patients to remain on protocol therapy through this initial event. The key component of the iRANO criteria is specific additional guidance for the determination of progressive disease in patients with neuro-oncological malignancies undergoing immunotherapy (Figure 1). Specifically, the iRANO criteria advocate for the confirmation of radiographic progression in appropriate patients defined by clinical status and time from initiation of immunotherapy.

If disease progression is confirmed on subsequent scan(s), then the date of progression is backdated to the original date of radiographic worsening.

Figure 1: iRANO treatment algorithm for the assessment of progressive imaging findings in patients with neuro-oncological malignancies undergoing immunotherapy [Okada *et al.*, 2015].

iRANO=immunotherapy Response Assessment in Neuro-Oncology.

In patients who have imaging findings that meet RANO criteria for progressive disease within 6 months of starting immunotherapy including the development of new lesions, confirmation of radiographic progression on follow-up imaging before defining the patient as nonresponsive to treatment might be needed provided that the patient does not have new or

substantially worse neurological deficits. Such patients might be allowed a window of up to 3 months before confirming disease progression with the scan that first showed initial progressive changes as the new reference scan for comparison with subsequent imaging studies.

If RANO criteria for progressive disease are met on the follow-up scan 3 months later, non-responsiveness to treatment should be assumed, and the date of progressive disease should be back-dated to the initial date when it was first identified (table 1). Patients who develop substantial new or worsened neurological deficits not due to comorbid events or a change in co-administered medication at any time within the 3-month follow-up window should be designated as non-responsive to treatment and should discontinue immunotherapy. For these patients, the date of actual tumor progression should also be back-dated to the date when radiographic progressive disease was initially identified.

If radiographic findings at the 3-month follow-up meet RANO criteria for stable disease, partial response, or complete response compared with the original scan meeting criteria for progression, and no new or worsened neurological deficits are identified, such patients should be deemed as deriving clinical benefit from therapy and allowed to continue treatment. Patients who develop worsening radiographic findings compared with the pretreatment baseline scan more than 6 months from starting immunotherapy are expected to have a low likelihood of ultimately deriving clinical benefit and should be regarded as non-responsive to treatment with a recommendation to discontinue therapy.

#### *11.4.3 Progression-free Survival*

RANO-BM proposes evaluating of progression-free survival according to a bi-compartmental model, i.e. each compartment (CNS and non-CNS) is evaluated separately, CNS according to RANO-BM and non-CNS according to RECIST 1.1. Progression in either compartment is deemed an overall progression event and site of first progression (CNS or non-CNS) is captured as a unique data element in the CRFs.

RECIST 1.1 uses instead a summation approach. With RECIST 1.1, up to 2 target lesions per organ may be assessed and the longest dimension of all target lesions (i.e. CNS and non-CNS) are summed for evaluation of response and progression. As with RANO-BM, unequivocal worsening of target lesions in either CNS or non-CNS compartments also constitutes a progression event. Unlike RANO-BM, RECIST 1.1 relies primarily on radiographic findings and does not include neurological status or corticosteroid use.

It is unknown what the correlation between RANO-BM and RECIST 1.1 is with respect to PFS and with respect to any relationships between PFS and OS. In this study, data will be collected prospectively to allow calculation of PFS according to both methods.

### 11.4.3 Definition of Abscopal response

As described previously, abscopal response is defined as a decrease in the longest diameter of at least 30% in any measurable ( $\geq 1$  cm) non-irradiated lesion from baseline [Golden *et al.*, 2015]. In patients with more than three lesions, the non-irradiated lesions will be measured individually for response to treatment. The best abscopal responding lesion will be reported.

#### 11.4.3.1 Definition of overall response according abscopal response definition

- Complete abscopal response is defined as the complete disappearance of a measurable non-irradiated lesion.
- Partial abscopal response is defined as at least a 30% decrease in the longest diameter.
- Progressive disease is defined as at least a 20% increase in the longest diameter of the best measurable non-irradiated lesion.
- Stable disease is defined as insufficient shrinkage or growth to qualify for a partial abscopal or complete abscopal response or progressive disease.

### 11.4.4 Patient-Reported Outcome Measure

#### 11.4.4.1 The PRO outcome measure for this study is as follows: Scores from the MDASI-BT assessment

### 11.4.5 Investigator-Assessed Neurological Evaluation

In order to standardize the evaluation of key neurological exam components, this study will use the Neurological Assessment in Neuro-Oncology (NANO) scale [Nayak *et al.*, 2014]. The scale was developed by an international group of neuro-oncologists convened bi-weekly between June 2012 and July 2013 as an objective and quantifiable metric of neurologic function evaluable during a routine office examination that will integrate into the existing RANO criteria [Lin *et al.*, 2015]. The NANO scale is intended to serve as a quick, oncology-friendly, quantifiable, evaluation of eight relevant neurologic domains based on direct examination by clinicians during routine office visits. The scale defines criteria for domain-specific and overall scores of response, progression and stable disease. In addition, a given domain is scored non-assessed if the clinician neglects to examine the domain or non-evaluable if the domain cannot be accurately assessed due to pre-existing conditions, co-morbid events, and/or concurrent medications.

### 11.4.6 EQ-5D evaluation

In order to evaluate the impact of the study treatment, on general health status we will have participants complete the EQ-5D questionnaire (APPENDICES E or F).

## 12. DATA REPORTING / REGULATORY REQUIREMENTS

Adverse event lists, guidelines, and instructions for AE reporting can be found in Section 7.0 (Adverse Events: List and Reporting Requirements).

## 12.1 Data Reporting

### 12.1.1 Method

ODQ will collect, manage, and perform quality checks on the data for this study.

### 12.1.2 Responsibility for Data Submission

Investigative sites within DF/HCC are responsible for submitting data and/or data forms to the ODQ according to the schedule set by ODQ.

### 12.1.3 Study close-out

Any study report submitted to the FDA by the overall PI will be copied to [REDACTED]. This includes all IND annual reports and the Clinical Study Report (final study report). Additionally, any literature articles that are a result of the study should be sent to [REDACTED].

All IND annual reports submitted to the FDA by the Sponsor-Investigator should be copied to [REDACTED]. Copies of such reports should be faxed to [REDACTED] Drug Safety: [REDACTED].

For Investigator-Initiated IND Studies, some additional reporting requirements for the FDA apply in accordance with the guidance set forth in 21 CFR § 600.80.

## 12.2 Data Safety Monitoring

The DF/HCC Data and Safety Monitoring Committee (DSMC) will review and monitor toxicity and accrual data from this study. The committee is composed of clinical specialists with experience in oncology and who have no direct relationship with the study. Information that raises any questions about participant safety will be addressed with the Overall PI and study team.

The DSMC will review each protocol up to four times a year or more often if required to review toxicity and accrual data. Information to be provided to the committee may include: up-to-date participant accrual; current dose level information; DLT information; all grade 2 or higher unexpected adverse events that have been reported; summary of all deaths occurring within 30 days of intervention for Phase I or II protocols; for gene therapy protocols, summary of all deaths while being treated and during active follow-up; any response information; audit results, and a summary provided by the study team. Other information (e.g. scans, laboratory values) will be provided upon request.

## 12.3 Multicenter Guidelines

N/A

## 12.4 Collaborative Agreements Language

N/A

## 13. STATISTICAL CONSIDERATIONS

### 13.1 Study Design/Endpoints

This is an open-label, single arm phase II study to assess PFS in patients with TNBC and brain metastasis who will receive stereotactic radiation in combination with atezolizumab. The target enrollment is 45 participants.

#### Primary endpoint

The primary endpoint is PFS defined as time from first dose of atezolizumab (day 1 cycle 1) to progression or death due to any cause. Progression will be defined according to the bi-compartmental model proposed in the RANO-BM publication and is defined as the first detection of radiologic progression of intracranial (per RANO-BM criteria; Section 11.1), extracranial (per RECIST 1.1 criteria; Section 11.2), or both or unequivocal progression of non-measurable disease in the opinion of the treating physician (an explanation must be provided); with each compartment (CNS and non-CNS) assessed separately.

#### Key secondary endpoints

Secondary endpoints include extracranial objective response rate (ORR), defined as an extracranial complete (CR) or partial (PR) response according to RECIST 1.1, and OS, defined as the time from the first dose of atezolizumab to death due to any cause.

### 13.2 Sample Size, Accrual Rate and Study Duration

The primary endpoint is bi-compartmental PFS according to RANO-BM criteria. A sample size of 45 was chosen to achieve 80 % power to detect a difference between the null hypothesis median PFS of 2 months and alternative of 3.5 months at a one-sided type I error of 0.05.

The null hypothesis was derived from two sources: First, a prospective trial testing the combination of irinotecan and iniparib in patients with metastatic triple-negative breast cancer and new/progressive brain metastases reported a median time to progression (which included both intracranial and extracranial progression) of 2.14 months [Anders *et al.*, 2014]. Next, in a retrospective study describing outcomes of breast cancer patients after initial stereotactic radiation, time to intracranial progression was significantly shorter in patients with triple-negative breast cancer, relative to the luminal A subtype (HR 28.0 in multivariable model,  $p=0.003$  [Dyer *et al.*, 2012]. Although the numbers are small, the point estimate for the time to intracranial progression in the triple-negative subset was 2.5 months [Dyer *et al.*, 2012].

Anticipated accrual of approximately 2 patients per month, it will require approximately 24 months of patient accession to reach 45 patients. The primary analysis of PFS and OS will be

time-driven and performed after 6 months of additional follow-up.

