### 13.5 Analysis of Primary Endpoint

The primary endpoint is bi-compartmental PFS defined as time from first dose of atezolizumab (day 1 cycle 1) to progression or death due to any cause. Progression is defined as the first detection of radiologic progression of intracranial (per RANO-BM criteria; Section 11.1), extracranial (per RECIST 1.1 criteria; Section 11.2), or both or unequivocal progression of non-measurable disease in the opinion of the treating physician (an explanation must be provided). The PFS will be analyzed using Kaplan–Meier product-limit estimates and will be plotted with two-sided 90% confidence bands using Greenwood’s formula for the variance. For evaluating median survival, a Brookmeyer-Crowley like test will be conducted using the one-sided  $\alpha = 0.05$ .

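### Primary PFS test: at N=45, under exponential PFS, the stated 80% power and one-sided 5% error do not both hold, and the version of the test is left open

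*Combined protocol and SAP*

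**What the plan says.** Section 13.2 sets the design for the primary endpoint: "A sample size of 45 was chosen to achieve 80 % power to detect a difference", for a "null hypothesis median PFS of 2 months and alternative of 3.5 months", "at a one-sided type I error of 0.05". Accrual takes about 24 months, and the analysis follows after 6 more months.

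Section 13.5 says "The PFS will be analyzed using Kaplan–Meier product-limit estimates", and that the curve "will be plotted with two-sided 90% confidence bands using" Greenwood's variance. The next sentence gives the test: "a Brookmeyer-Crowley like test will be conducted using the one-sided" 0.05 level. That sentence names no variance, transformation or cut-off.

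Neither section states a distribution for PFS or an allowance for early dropout. An exponential form appears only in Section 13.6.2, for OS. Section 13.6.1, by contrast, specifies an exact binomial test with one-sided error of at most 0.05 for extracranial response.

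**The concern.** A Brookmeyer-Crowley test of a 2-month median compares the Kaplan-Meier estimate at 2 months with 0.5. Every patient has at least 6 months of potential follow-up, so there is no administrative censoring before 2 months. Without early dropout the estimate is a simple proportion out of 45, and the test can reject only at whole-number counts. Its real error rate and power may then differ from the large-sample values, and different forms of the test may have different cut-offs.

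At stake is the trial's primary conclusion. Either its false-positive rate is above the stated 5%, or its power is below the stated 80%. For one possible result, the answer depends on a choice that could be made after the data are seen.

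**Working it through.** **Inputs.** N=45, medians of 2 and 3.5 months, one-sided 0.05, stated power 80% (Section 13.2); median test and Kaplan-Meier estimates (Section 13.5). Assumed here: exponential PFS, and at first no censoring before 2 months.

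**Event-free probability at 2 months.** Null: 0.5. Alternative: 0.5^(2/3.5) = 0.673.

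**Step 1: reproduce the 80%.** Normal approximation with the variance at the alternative:

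- SE = √(0.673 × 0.327 / 45) = 0.0699
- (0.673 − 0.5) / 0.0699 = 2.473
- Power = Φ(2.473 − 1.645) = 79.6%

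The printed figure is reproduced.

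**Step 2: find the cut-off of each version.** For x of 45 event-free, p = x/45:

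- Plain (Greenwood): z = (p − 0.5) / √(p(1 − p)/45)
- Null variance: z = (p − 0.5) / √(0.25/45)
- Log-log: z = [log(−log 0.5) − log(−log p)] / [√((1 − p)/(45p)) / |log p|]

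| x | Plain | Null variance | Log-log |
|---|---|---|---|
| 28 | 1.691 | 1.640 | 1.548 |
| 29 | 2.024 | 1.938 | 1.809 |

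Against 1.645, the plain version rejects from 28 and the other two from 29. The exact binomial test also needs 29, as Step 3 shows.

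**Step 3: exact size and power, X ~ Binomial(45, p).**

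| Rule | Size (p = 0.5) | Power (p = 0.673) |
|---|---|---|
| ≥28 | 6.76% | 81.3% |
| ≥29 | 3.62% | 71.8% |

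No whole-number cut-off lies between them. Exactly 28/45 has probability 3.1% under the null and 9.4% under the alternative.

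**Step 4: cross-check against the OS power table.** Section 13.6.2 uses the same N and test, with a null median of 5 months; the probability of being alive at 5 months is 0.5^(5/median).

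| Median OS (months) | Printed | ≥28 | ≥29 |
|---|---|---|---|
| 10 | 90% | 91.9% | 86.1% |
| 8.33 | 75% | 75.7% | 65.1% |
| 8 | 70% | 70.4% | 59.0% |
| 7.5 | 61% | 60.8% | 48.7% |

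The printed powers follow the ≥28 rule, which suggests that the planning figures belong to the version whose size exceeds 5%.

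**Step 5: early censoring.** Simulation with 24 months of accrual, 6 months of follow-up, exponential PFS and an assumed share lost before 2 months:

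| Censored early | Plain: size / power | Log-log: size / power |
|---|---|---|
| 0% | 6.7% / 81% | 3.6% / 72% |
| 2% | 5.9% / 79% | 3.9% / 72% |
| 5% | 5.5% / 77% | 4.0% / 72% |
| 10% | 5.5% / 76% | 4.0% / 71% |

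Neither version meets both printed figures in any row.

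**Step 6: shape of the PFS curve.** For Weibull PFS with the same medians, the event-free probability at 2 months under the alternative is 0.5^((2/3.5)^k). The size is unchanged because the null fixes it at 0.5.

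| Shape k | Power of ≥29 |
|---|---|
| 0.8 | 55% |
| 1.0 | 72% |
| 1.1 | 79% |
| 1.15 | 82% |
| 1.2 | 84% |

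**The case against.** The strongest reply is that nothing was miscalculated. The plan gives a nominal alpha and a large-sample power, and any discrete test has an exact size that differs from its nominal level. Where the plan intends exact control, in Section 13.6.1, it says so. This stands in part: a reader might infer an arithmetic slip in the 80%, and Step 1 shows there is none. But Section 13.2 states the 0.05 without qualification, and the rule that delivers the 80% runs about a third above it (6.76/5 = 1.35).

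Second, a reader might infer that the plan has adopted a 6.8% test because Greenwood is named in Section 13.5. The text does not support that. Greenwood is attached to the plotted bands, and the test may well be run in a form that holds 5%. What stands is that the choice is open.

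Third, a reader might infer that 5% and 80% are incompatible at N=45 whatever the data look like. That is too strong. The plan states no PFS distribution, and the ≥29 rule passes 80% power at a Weibull shape between 1.1 and 1.15. Equally, a shape of 0.8 brings it down to 55%.

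Fourth, early withdrawal and loss to follow-up are possible (Sections 5.5 and 5.7) and bring the plain version's excess over 5% down to about half a point. Its power then falls below 80%, so the point becomes smaller but remains.

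**Conclusion.** The point holds, conditionally. Under exponential PFS and no censoring before 2 months, the median test at N=45 has either size 6.8% with power 81%, or size 3.6% with power about 72%. Under exponential PFS, neither the plain nor the log-log version met both stated figures with 0–10% early censoring. The size figures need only a true 2-month median and no early censoring; the 72% also needs the exponential form.

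The practical weight is moderate. The size excess is 1.8 percentage points at most, and the power shortfall about 8 points in the central case. The outcome on which the versions disagree is uncommon, but it would decide the primary result. The documents do not support reading this as a flaw that requires a larger trial.

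**What to change.** In Section 13.5, pre-specify one version of the test that holds 5%: log-log or exact. State that it rejects with at least 29 of 45 event-free at 2 months if nobody is censored earlier.

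In Section 13.2, restate power at a 3.5-month median as about 72% under exponential PFS. Name that assumption, and give the range of 55% to 84% for Weibull shapes 0.8 to 1.2. The actual size of 3.6% without early censoring can be given alongside.

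Section 13.6.2 uses the same test wording for OS. If the chosen version is carried over to OS, the power table there needs the same check.

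The cost is wording only, with no extra patients or procedures. One printed figure becomes less favourable. The change should be made before the outcome data are seen.
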